9.7.2.3. Sensitivity analyses

To ensure the robustness of the results, we will conduct sensitivity analyses to address the potential misclassification of the outcomes, potential unobserved confounders, and potential selection bias. When conducting the propensity score matching, we will use the nearest neighborhood matching with caliper width equal to 0.01 of the propensity score as the primary choice [Austin, 2010]. Other choices of caliper (i.e., 0.02 to 0.051) will also be compared to strike a desirable balance between the sample size and balances of baseline characteristics. Detailed sensitivity analyses and assessment of potential biases are documented in the SAP.

9.7.3. Descriptive Analysis

If the feasibility assessment (Section 9.6.1.1) identifies that the number of HZ/su-exposed live birth pregnancies identified during the feasibility assessment is less than one third of the number of HZ/su-exposed live birth pregnancies needed for the cohort study, a descriptive analysis will be conducted among all HZ/su-exposed pregnancies and their matched comparators. Prevalence and 95% CIs of MCMs and additional infant/birth, complications of pregnancy, and pregnancy outcomes will be estimated in the matched HZ/su-exposed and unexposed cohorts. Additional analyses will not be conducted.

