9.2.1.2. HZ/su-Exposed Group (Amended 15 August 2022)

Among the eligible cohort of live birth pregnancies linked to an infant (Primary Objective and Secondary Objective 1 cohort) and among the cohort of all eligible *live birth and non-live birth* pregnancies (Secondary Objective 2 cohort), women with IC conditions exposed to HZ/su during pregnancy will be identified. Exposure will be further categorized by stage of pregnancy: pre-pregnancy, first trimester, second trimester, and third trimester. The first trimester of pregnancy will be defined as 0 to < 14 weeks gestation, the second trimester as 14 to < 28 weeks, and the third trimester as 28 weeks through the end of the pregnancy.

A 30-day pre-pregnancy period (prior to LMP) will be included. There is no safety signal that would indicate that there is a risk pre-pregnancy. However, published vaccine safety studies have included varying pre-pregnancy periods [Kerr, 2020, Kharbanda, 2021, Panagiotakopoulos, 2020]. More recently published studies have included no pre-pregnancy or up to a 42-day pre-pregnancy period.

214420 (EPI-ZOSTER-039 VS US DB) Protocol Amendment 2 Final

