9.5. Study size

All pregnancies among women who meet the study inclusion/exclusion criteria will be included in this study.

As the IC conditions included are heterogeneous and the number of MCMs for the primary outcome is likely small, the prevalence of each MCMs among each IC condition under study is not available. For sample size calculation for the cohort study, we employed the prevalence of overall MCMs (3%) in the general population [Holmes, 1976; Leppig, 1987; Marden, 1964; Van Regemorter, 1984] which might have a lower prevalence than among women with IC conditions. Therefore, the sample size calculated is relatively conservative. Assuming a 1:3 ratio of HZ/su-exposed to unexposed, a type 1 error of 0.05, and a target risk ratio of 2.0 for the primary safety outcome of MCMs, 711 live birth infants (live birth pregnancies linked to infant records) from the HZ/su-exposed group and 2133 live birth infants from the unexposed group will allow us to achieve 90% power.

The Power Analysis and Sample Size software (NCCS Statistical Software) was used in the sample size calculation.

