9.7.1. Characterization of Use of HZ/su and IC Conditions During Pregnancy

Annual descriptive analyses to estimate the counts of HZ/su exposed pregnancies among women with IC conditions will be performed. Data from the first two years will be used to determine the feasibility of a full-scale cohort study (see Section 9.6.1.1). Analyses will be performed in the cohort of pregnant women aged 18 to 49 years diagnosed with IC conditions meeting health plan enrollment (medical and pharmacy benefits) inclusion criteria. The analysis will be conducted for pregnancies resulting in live births. The counts of pregnancies exposed to HZ/su overall and in each trimester (including a 30-day pre-pregnancy period) will be estimated. Counts of pregnancies unexposed to HZ/su will be tabulated by maternal age, calendar year of pregnancy outcome, and IC condition. Similarly, counts of women of childbearing age (18 to 49 years) exposed to HZ/su with IC conditions will be estimated.

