9.7.2. Cohort Study

If the feasibility assessment (Section 9.6.1.1) identifies that the number of HZ/su-exposed pregnancies is equal to or above the target number of exposed pregnancies, a subsequent cohort study will be conducted.

Infant/birth outcomes and pregnancy complications will be assessed among eligible live birth pregnancies linked to infant records. Pregnancy outcomes will be assessed in the population of all pregnant women meeting eligibility criteria.

Propensity scores and matching will occur within each Data Partner. Potential confounders are described in Section 9.3.3. The methodology will be described in detail in the Statistical Analysis Plan (SAP).

9.7.2.1. Primary Objective and Secondary Objective 1

The Mantel-Haenszel Chi-square test or Fisher exact test (univariate analysis), wherever appropriate, will be employed to compare the prevalence of the primary outcome (MCMs) between eligible live birth pregnancies among women with IC conditions who were vaccinated with HZ/su during pregnancy and those who were not vaccinated with HZ/su during pregnancy. Multivariable conditional logistic regression will be conducted to adjust for potential residual confounding after matching if there is statistical significance in univariate analysis. In addition, the prevalence of MCMs and their associated 95% CIs will be calculated among women with IC conditions who were exposed to HZ/su during pregnancy versus the corresponding matched women who were not exposed to HZ/su during pregnancy. All analyses will be stratified by stage of pregnancy (pre-pregnancy, first trimester, second trimester, third trimester).

Similar methods will be used for each of the secondary infant/birth outcomes (e.g., preterm birth, SGA, LBW, NICU admission, neonatal death).

9.7.2.2. Secondary Objective 2

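### Section 9.7.3 gives the descriptive fallback no breakdown by stage of exposure and bars further analyses, while the Abstract and Section 9.7.2 stratify all analyses by stage

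*Protocol*

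**What the plan says.** Section 9.7.3 defines the fallback population broadly: "a descriptive analysis will be conducted among all HZ/su-exposed pregnancies and their matched comparators". For malformations and all other outcomes, prevalence and 95% CIs "will be estimated in the matched HZ/su-exposed and unexposed cohorts. Additional analyses will not be conducted". No stage of exposure is mentioned.

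Elsewhere in the protocol, stage is built in:

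- Section 9.2.1.2: "Exposure will be further categorized by stage of pregnancy: pre-pregnancy, first trimester, second trimester, and third trimester". The same section extends exposure backwards: "A 30-day pre-pregnancy period (prior to LMP) will be included".
- Section 9.7.1, on exposed live-birth pregnancies: "The counts of pregnancies exposed to HZ/su overall and in each trimester (including a 30-day pre-pregnancy period) will be estimated". These are counts of exposures, not outcomes.
- Section 9.7.2.1, for the cohort study: "All analyses will be stratified by stage of pregnancy (pre-pregnancy, first trimester, second trimester, third trimester". Section 9.7.2.2 and the data-analysis paragraph of the Abstract carry the same sentence.

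The Abstract and Section 8 describe the fallback as involving no statistical comparisons.

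**The concern.** The full cohort study would show malformation prevalence separately for infants exposed before LMP and in each trimester. The fallback, as worded, would not, and its last sentence leaves an analyst no clear mandate to add those rows. The fallback may well be the final report, since Section 7 expects very few pregnancy exposures and Section 9.6.1 expects a small number. It makes no comparison, so the prevalences and their intervals are the whole result.

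Two things are at stake. If risk is raised only after first-trimester exposure, a figure pooled over all stages is pulled toward background. And the pooled interval rests on more infants than the first-trimester group contains, whether or not there is an effect. For spontaneous abortion there is also a denominator problem that needs no assumed effect.

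**Working it through.** **Where the fallback applies.** Section 9.6.1.1 sets the threshold at one third of 711: 711 / 3 = 237, which reproduces. The fallback therefore has at most 236 exposed linked live births.

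**Inputs.** Background malformation prevalence 3% and target risk ratio 2.0 (Section 9.5). Assumptions not in the documents: the ratio of 2.0 applies to first-trimester exposure only, the ratio is 1 at every other stage, and a share f of exposures falls in the first trimester.

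**Dilution.** Pooled prevalence = f × 6% + (1 − f) × 3% = 3% × (1 + f), so the pooled ratio is 1 + f. Intervals are exact (Clopper-Pearson) for 236 exposed, with expected events rounded to whole infants.

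| f | Pooled prevalence | Pooled ratio | Pooled events, 95% CI | First-trimester events, 95% CI |
|---|---|---|---|---|
| 0.80 | 5.4% | 1.8 | 13/236, 3.0 to 9.2% | 11/189, 2.9 to 10.2% |
| 0.60 | 4.8% | 1.6 | 11/236, 2.3 to 8.2% | 9/142, 2.9 to 11.7% |
| 0.50 | 4.5% | 1.5 | 11/236, 2.3 to 8.2% | 7/118, 2.4 to 11.8% |
| 0.40 | 4.2% | 1.4 | 10/236, 2.1 to 7.7% | 6/94, 2.4 to 13.4% |
| 0.25 | 3.75% | 1.25 | 9/236, 1.8 to 7.1% | 4/59, 1.9 to 16.5% |

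A first-trimester row would be expected to show 6% at every f. With no first-trimester effect, the pooled point estimate is not diluted at any f.

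**Precision with no events.** The exact upper 95% limit is 1 − 0.025^(1/n).

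- n = 200 (an illustrative total below 237): 1.83%.
- n = 100 (half of them first trimester): 3.62%.

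This is an extreme case, since 200 × 3% = 6 events would be expected at background. It isolates the difference in precision.

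**Spontaneous abortion.** Section 9.3.2.2 defines it as a loss before 20 weeks. Section 9.2.1.2 starts the third trimester at 28 weeks and runs the second from 14 to under 28. A pregnancy exposed after 20 weeks is in the pooled denominator but cannot have the event. If a share g is exposed that late, the pooled prevalence is (1 − g) times that among pregnancies exposed earlier: 0.90 times at g = 10% and 0.75 times at g = 25% (both assumed). Section 9.2.1.3 requires comparators to have reached the same gestational week, so the same shrinkage affects both groups. The absolute prevalences are lowered; the contrast need not be.

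**The case against.** Section 9.7.3 never says the prevalence is one pooled figure. It names the measure and the cohorts, while Section 9.2.1.2 assigns a stage to every exposed pregnancy, whichever route the study takes. The Abstract's sentence on stratifying all analyses can be read to reach the fallback, in which case 9.7.3 is merely terse. The closing bar may only restate that no comparisons are made, and Section 9.7.4 leaves detailed methodology to the SAP, which is not shown. The primary objective concerns exposure during pregnancy, with no first-trimester restriction, so an overall figure does answer it.

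Much of this stands. A reader might infer that the protocol expressly commits to a single pooled figure; it does not. A reader might also infer that the fallback overstates reassurance as a matter of course. The documents do not support that: it takes a real first-trimester effect and a material share of exposures at other stages. Section 7 describes vaccination before the woman knows she is pregnant, which points to early exposure and modest dilution, although the 30-day window before LMP works the other way. Even at f = 0.5 the pooled interval of 2.3 to 8.2% still contains 6%, so it would not exclude a doubling.

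What does not stand is leaving the text alone. If the Abstract's sentence covers the fallback, it sits badly with a bar on additional analyses. If it does not, the fallback has no stage breakdown. The Abstract and Section 8 already rule out comparisons, and the words in 9.7.3 are broader than that. This is a stated prohibition rather than a detail left open for the SAP, and Section 9.7.4 itself says that major changes to the primary endpoint analyses would be reflected in a protocol amendment. The counts in Section 9.7.1 would show the mix of stages, but no outcomes by stage.

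**Conclusion.** The point holds as an unresolved inconsistency with a practical consequence. On a plain reading, the fallback yields no stage-specific malformation prevalence, although the exposed group spans 30 days before LMP and all three trimesters.

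The size is conditional. A true first-trimester ratio of 2.0 would appear as 1.25 to 1.8 for first-trimester shares of 25% to 80%, given 3% background and no effect elsewhere. The effect pattern and the shares are assumptions. The difference in precision needs no effect: 1.8% against 3.6% in the zero-event illustration. The pooled interval is correct for the pooled group; it should simply not be read as the precision for first-trimester exposure. The spontaneous-abortion denominator problem follows from the protocol's own definitions, and its size depends on the undocumented share exposed after 20 weeks.

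**What to change.** Reconcile Section 9.7.3 with the Abstract:

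- Report prevalence and 95% CIs overall and by the four stages of Section 9.2.1.2, with each comparator taking the stage of its matched exposed pregnancy.
- Show first-trimester malformation prevalence as its own row, and flag sparse strata.
- For spontaneous abortion, note that pregnancies exposed after 20 weeks cannot have the event. The stage rows separate the third trimester, but the second-trimester row still straddles 20 weeks.
- Limit the closing sentence to statistical comparisons and analyses beyond these.

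The cost is a short edit and some table rows from a variable already derived. The overall row stays and no test is added. Because the vaccine has two doses, the text should also say where a pregnancy with doses in two stages is counted. The downside is wide stage-specific intervals (1.9 to 16.5% for 4 events in 59 infants, for example) and some sparse cells.

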9.7.4. Statistical Analysis Plan

Detailed methodology for summary and statistical analyses of data collected in this study including sensitivity analyses and assessment of potential biases will be documented in a SAP, which will be dated, filed, and maintained by the sponsor. The SAP may modify the plans outlined in the protocol; any major modifications of primary endpoint definitions or their analyses would be reflected in a protocol amendment.

9.8. Quality control

As described above, the distributed network utilizes a common data model that enables data standardization across DPs. Furthermore, each of the participating DPs has experience with this data model given its role as an active participant in the Sentinel System. This study will use the same data quality assurance procedures as the Sentinel

214420 (EPI-ZOSTER-039 VS US DB)
Protocol Amendment 2 Final

[figure not shown]
System and the same curated datasets used by FDA to conduct Sentinel analyses. The quality assurance approach assesses consistency with the SCDM, evaluates adherence to data model requirements and definitions, evaluates logical relationships between data model tables, and reviews trends in medical and pharmacy services use within and across DPs. Full quality assurance processes and details on the Sentinel data curation approach are documented on the Sentinel website [Sentinel Initiative, 2021]. The data curation approach is consistent with guidance set forth by the FDA in its current recommendations for data quality assurance, specifically, "Guidance for Industry and FDA Staff: Best Practices for Conducting and Reporting Pharmacoepidemiologic Safety Studies Using Electronic Healthcare Data" (Guidance), section IV.E "Best Practices – Data Sources: QA and Quality Control", published in May 2013 [FDA, 2013].

The Quality Assurance procedures used in this study are the same as used for the FDA Sentinel Initiative. Further details about these procedures can be found on the Sentinel Initiative website.

In addition to quality assurance of data elements, HPHCI adopts standard SAS programming quality assurance and quality control processes used by the Sentinel System to check SAS programs and deliverables. Figure 3 illustrates the SOPs for SAS programming quality assurance and quality control in the Sentinel System.

By signing onto this protocol, the investigators agree to be responsible for implementing and maintaining a quality management system with written development procedures and functional area SOPs to ensure that studies are conducted, and data are generated, documented, and reported in compliance with the protocol, accepted standards of Good Clinical and Pharmacoepidemiology Practice, and all applicable federal, state, and local laws, rules and regulations relating to the conduct of the study.

Figure 3 Standard Operating Procedure for SAS Programming Quality Assurance and Quality Control in the Sentinel System

9.9. Limitations of the research methods

9.9.1. Limitations of the research methods

Several limitations are inherent in the conduct of studies of vaccine exposures during pregnancy with healthcare databases. The algorithms used to define data study variables may be imperfect and these rely on the accuracy and precision of coding for these items. As a result, misclassification of exposures, outcomes, and potential confounders can occur. In addition, only medically attended events are recorded in the healthcare database, thereby missing events without medical attendance such as early spontaneous abortions. Early fetal losses are often not captured in claims databases (or other data sources) but are generally reported to be mainly associated with chromosomal abnormalities [Zhang, 2018], which would likely not be related to vaccine exposures. In addition, some secondary outcomes of interest will be rare and may be difficult to assess within the study period (e.g., neonatal death). Neonatal deaths will only be captured in hospital discharge data which may lead to under ascertainment of this outcome.

Although appropriate methodologies (e.g., propensity score matching) will be applied to statistically adjust for differences between exposed pregnancies versus unexposed

214420 (EPI-ZOSTER-039 VS US DB) Protocol Amendment 2 Final

pregnancies in this study, it is possible that residual confounding may be present. In addition, depending on the number of events observed, we may be limited in the ability to include additional covariate information in regression models. Some potential covariates are incompletely captured in the health plan data, e.g., over-the-counter (OTC) folate intake, alcohol use, and tobacco use. This limitation relates to the constraint about claims databases. Some confounders (e.g., alcohol use) will not be completely captured although we do not expect the capture will differ by the exposure. We will conduct a sensitivity analysis to exclude such variables and treat them as unmeasured confounders. A detailed description of the bounding factor is provided in the SAP Section 8.7.1 to estimate the magnitude of effect of an unobserved confounder needed to change the statistical inference. We will also compare the results with and without such covariates.

The linkage of the infants to their mothers has been found to be approximately 70-80% and infants without linkage to their mothers will not be included in current study. Another potential for selection bias exists given that we will evaluate the risk of MCMs (primary outcome of interest) and other infant outcomes among only live births. Specifically, a bias may result if the exposure is associated with pregnancy loss (competing events). Sensitivity analyses and assessment of potential biases are planned and will be detailed in the SAP.

An important potential limitation of the study is that an adequate sample size might be difficult to achieve for a cohort study. Thus, a feasibility assessment will be conducted to determine whether it is practical to conduct the cohort study. If an inadequate number of exposed live births are identified in the feasibility assessment, a descriptive analysis of the prevalence of infant and pregnancy outcomes will be conducted.

Lastly, the results of this study may not be generalizable to patients who receive care in very different health systems in the U.S., and may only represent the commercially insured patient population in the U.S.

9.9.2. Strengths of research methods

To mitigate the effect of these limitations the study will use well-recognized algorithms and methods for identification of pregnancies, pregnancy outcomes, and potential confounders of interest, with preference for using the same methods as those used within the FDA Sentinel System. We will also conduct sensitivity analyses and methods to assess and/or control for potential selection bias (i.e., bias introduced when competing events are examined separately).

Using electronic healthcare data to assess the risk of birth and pregnancy outcomes after exposure to HZ/su overcomes many challenges associated with conducting a traditional pregnancy registry. The electronic healthcare data approach differs from a traditional pregnancy registry that passively collects information on women exposed to the product in a prospective format. The traditional pregnancy registry may fail to provide clinically meaningful information because of selection bias due to the limited number of pregnant women voluntarily enrolled in the registry, difficulty in recruiting an appropriate comparison group, and loss to follow-up. Using electronic healthcare data with a well-defined population can overcome some limitations of the traditional pregnancy registry.

214420 (EPI-ZOSTER-039 VS US DB) Protocol Amendment 2 Final

Biases may be reduced as most exposures during pregnancy would be captured in the database and exposed and unexposed groups have been identified from the same source population. In addition, ascertainment of important study outcomes like spontaneous abortion and stillbirth may be improved. Medical record review of MCMs further improves ascertainment of valid data for the primary outcome of interest. Collectively, this study design improves validity and interpretability of the study results. This method is more efficient, complete and objective in data collection than self-reporting; therefore, it may lead to less information bias with higher data quality.

9.10. Other aspects

Not applicable.

10. PROTECTION OF HUMAN SUBJECTS

10.1. Patient information and consent

All parties will ensure protection of patients' personal data and will not include patient names on any sponsor forms, reports, publications, or in any other disclosures, except where required by law. In case of data transfer, high standards of confidentiality and protection of patient personal data will be maintained.

The study will be conducted with a waiver of informed consent. This study will involve numerous individuals from multiple health plans and delivery systems. Thus, it could not be practically conducted without a waiver of informed consent. The proposed study has minimal risk; potential breaches of privacy and confidentiality are the primary study risks These risks will be minimized by ensuring that rigorous security procedures are applied to data collection, management, and transfer. Some of these procedures include using a study identification number in place of direct patient identifiers; transferring data using secure, encrypted websites; and ensuring that appropriate data transfer agreements are in place between institutions prior to data sharing. Additionally, only trained and authorized study staff will be allowed to access study data Secure data storage methods, such as password-protected electronic files and locked paper files, will be used by all participating DPs and the data Coordinating Center at HPHCI.

